##### **B5.2 Research Subjects/Population(s)**

###### **B5.2.1 Subject Population(s)**

Twenty healthy, recreationally-active adult men and women representative of active duty military service members will be tested in this study. This study will recruit up to 70 individuals in order to complete testing on 20. These individuals may be recruited from the HRV population, civilians, and active duty military personnel (on and off the installation).

###### **B5.2.2 Number of Subjects, Records, and/or Specimens**

In previous studies of similar design, pre-study screening failure rate is approximately 25%. To account for screening failures and the possibility that actual study attrition rates may be greater, we estimate that 30 individuals will require screening in order to complete testing on the 20 volunteers necessary to reach statistical power in our primary outcomes. All screening will stop once complete data has been collected on 20 volunteers. Records and specimen collection are described in the Research Procedures and Data Collection sections. During briefings and consenting, potential participants will be informed that even though they may be eligible and want to participate, if we are able to obtain enough data from preceding subjects, they may not ultimately be tested.

### **B5.2.3 Inclusion Criteria**

- Men and women aged 18 – 35 years
- Body mass index < 30.0 kg/m^2
- Healthy without evidence of chronic illness or musculoskeletal injury as determined by the USARIEM Office of Medical Support and Oversight (OMSO)
- Resistance exercise trained defined by self-report as performing ≥ 2 sessions/wk for previous 6 mo
- Refrain from taking any nonsteroidal anti-inflammatory drugs (e.g., aspirin, Advil®, Aleve®, Naprosyn®), or any other aspirin-containing product for 10 days before starting and at least 5 days after completing the study
- Willing to refrain from alcohol, smoking any nicotine product (includes e-cigarettes); vaping, chewing tobacco, caffeine, and dietary supplement use throughout the entire study period
- Supervisor approval for federal civilian employees and non-HRV active duty military personnel working within the US Army Natick Soldier Systems Center

### **B5.2.4 Exclusion Criteria**

- Musculoskeletal injuries that compromise exercise capability as determined by the USARIEM Office of Medical Support and Oversight (OMSO)
- Metabolic or cardiovascular abnormalities, gastrointestinal disorders (e.g., kidney disease, diabetes, cardiovascular disease, etc.)
- Abnormal PT/PTT test or problems with blood clotting
- History of complications with lidocaine
- Present condition of alcoholism, anabolic steroids, or other substance abuse issues
- Blood donation within 8-wk of beginning the study
- Pregnancy (self-report or results of urine pregnancy test before body composition testing)
- Unwillingness or inability to consume study diets or foods provided

## **B5.3 Research Procedures**

### **Experimental Design**

[figure not shown]
Twenty resistance-trained adults will be tested in this approximately 39-d randomized, double-blind cross-over study. Volunteers will participate in two, non-consecutive 5-d controlled energy deficit periods, separated by a 14-d washout period (i.e., sufficient time to restore nitrogen and metabolic homeostasis after moderate weight loss) [35-38]. Basal (fasting/resting), resting and post-resistance exercise (single leg exercise model) whole-body protein turnover and skeletal muscle protein synthesis responses to standard (0.10 g/kg) and high (0.30 g/kg) EAA doses will be determined the morning after completing each 5-d energy deficit. To limit potential confounding effects of pre-study diet, and to be consistent with our previous research [16, 39, 40], volunteers will be provided a 3-d run-in, eucaloric diet. After the 3-d eucaloric run-in diet, energy intake will be reduced by 30%. Physical activity will be completely restricted during the 3-d run-in diet and 5-d energy deficit to isolate the effects of the energy deficit on protein turnover and limit any residual effects of previous exercise on outcome measures [41].

The 30% energy deficit from diet alone is consistent with our previous energy deficit studies [42] and work demonstrating that a 10-d, 20% diet-induced energy deficit (i.e., ~500 kcal/d) downregulates resting skeletal muscle protein synthesis by as much as 19% [43]. Others have shown that 5-d of moderate energy deficit (reducing energy availability from 50 kcal/kg fat-free mass to 30 kcal/kg fat-free mass) is long enough to downregulate resting skeletal muscle protein synthesis by 27% [35]. In that study, ingesting 15 g and 30 g of whey protein isolate after a bout of resistance exercise restored muscle protein synthesis rates to resting, fasting rates observed during energy balance in a dose dependent manner. This proposal will extend these findings and determine if the observed muscle protein synthetic plateau after conventional resistance exercise [9] during energy balance persists during moderate energy deficit when EAA are ingested relative to body mass (0.10 g/kg versus 0.30 g/kg). Relative EAA intakes were chosen to minimize inter-subject variability and to provide a spectrum of responses to varying absolute EAA doses in order to delineate the breakpoint, and practical dose, at which skeletal muscle and whole-body anabolic responses are optimal [44]. This study will be the first to assess whole-body protein kinetics in response to consuming different doses of EAA and their associations with muscle protein synthesis during short-term energy deficit.

The stable isotope infusion protocol will occur in the morning following an overnight fast (**Figure 6**). Two intravenous catheters will be placed; one for the infusion of stable isotopes, and the other heated for serial “arterialized” blood sampling. As previously described [45], a baseline blood sample will be drawn (0-min) prior to primed continuous infusions of L-[ring-H5]-phenylalanine and L-[3,3-H2]-tyrosine. To appropriately reach isotopic equilibrium of L-[ring-H4] tyrosine enrichment derived from L-[ring-H5]-phenylalanine tracer, a priming dose of L-[ring-H4]-tyrosine also will be injected at 0-min [45]. All isotopes will be purchased from Cambridge Isotope Laboratories (CIL, Andover, MA) and solutions will be constituted by a licensed pharmacy and certified sterile and pyrogen free before administration (pharmacy to be determined).

At 120-min, a muscle biopsy of the vastus lateralis will be taken on the non-exercised leg only to assess basal (fasting/resting) muscle protein kinetics. After the muscle biopsy, volunteers will remain rested until they perform a heavy-load, high volume, single leg-resistance exercise bout at 195-min that consists of 8 sets X 10 repetitions on the leg-press and leg-extension machines [9]. Both exercises will be performed at 80% of a pre-determined one repetition maximum (1RM) with a 2-min rest interval between sets. Volunteers will have ~45-min to complete the exercise bout. In the event the volunteer is unable to complete the prescribed workload; the workload will be reduced by 4.5 kg as previously described [9]. This will be repeated until the participant can complete the prescribed work. Approximately 5-min after completing the exercise bout (240-min), a muscle biopsy will be taken from the vastus lateralis of the exercised and non-exercised (rested) legs (the exercised and non-exercised leg will be the same between trials). Immediately after the biopsies, volunteers will consume the appropriate dose (i.e., an artificially flavored beverage) of free-form EAA in 5-10-min [Reginator™; EAA content per 10 g of the mixture: 0.15 g histidine, 3.66 g leucine, 0.94 g isoleucine, 1.65 g lysine, 0.3 g methionine, 0.63 g phenylalanine, 0.89 g threonine, 0.1 g valine, 0.006 g tryptophan, and 0.81 g arginine (conditionally essential under stress)]. The phenylalanine content of the beverage will be artificially

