#### **B5. RESEARCH PLAN**

##### **B5.1 Research Design**

This study will be a randomized, double-blind, cross-over controlled trial. Before the study begins, a research team member ([name]) will generate the randomization scheme using a random number generator (<http://randomization.com>). [name] will be responsible for preparing and coding the individualized EAA drinks for each trial and she will hold the randomization code until the study has been completed (i.e., data collected and analyzed). The study investigators will be blinded to this process. The code will be broken by [name] after the primary outcomes (i.e., muscle protein synthesis and whole-body protein balance) have been statistically analyzed by the study investigators (i.e., [name], [name], [name], [name], [name], and [name]).

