### **3-d Run-In and 5-d Energy Deficit**

Volunteers will complete a baseline, pre-study 3-d diet record (**Appendix A**) and a 3-d activity log (**Appendix B**) according to instructions provided by study team dietitians. The data will be analyzed using Food Processor SQL™ (Salem, OR Version 10.0) and collected to predict volunteers' total daily energy requirements for the 3-d eucaloric run-in and 5-d energy deficit diets. The volunteers will receive standardized meals derived primarily from military combat rations (Meals Ready-to-Eat, MRE) for each diet phase to replicate the source of nutrition during short-term military operations. The energy content and macronutrient distribution of the MRE-based, 3-d run-in diet will be sufficient to maintain body weight and provide between 50-65% carbohydrate and  $1.6 \pm 0.2$  g protein·kg·d, amounts habitually consumed by Warfighters in past USARIEM studies [39, 42]. Total energy content of the 5-d energy deficient diet will be reduced by 30%, primarily by reducing the total amounts of carbohydrate and fat consumed, while keeping dietary protein constant at  $1.6 \pm 0.2$  g protein·kg·d. All meals will be prepared and provided to volunteers by study team dietitians during the 3-d run-in diet. During the 5-d energy deficit, all meals will be prepared and provided to the volunteers.. Volunteers will be completely restricted from all non-study physical activity during the 3-d run-in and 5-d energy deficit diets to minimize complications and the potential for carryover effects on study parameters. If necessary, military volunteers will be provided study-specific profiles to restrict physical activity. This approach has been applied successfully in past USARIEM studies [39].

During the 14-d washout period, volunteers will be instructed to consume an ad libitum diet. Routine physical activity (exercise) can be resumed during the wash-out phase at levels consistent with amounts reported in pre-study 3-d activity records. Diet records (24-h) and activity logs (24-h) will be completed every third day and then reviewed (the following day) during the 14-d washout period to assess dietary intake and physical activity. Volunteers will meet with study dietitians to review these records.

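### Trial 2 exercise loads are not tied to trial 1 and completed work need not be logged, which leaves avoidable noise and a possible order effect in the exercised-leg comparison (minor)

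*Combined protocol and SAP*

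**What the plan says.** B5.3, Experimental Design, prescribes a single-leg bout of eight sets of ten on leg press and leg extension.

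- **Starting load:** "Both exercises will be performed at 80% of a pre-determined one repetition maximum (1RM) with a 2-min rest interval between sets". No re-test of the 1RM before trial 2 is described.
- **If the volunteer cannot manage it:** "the workload will be reduced by 4.5 kg as previously described [9]. This will be repeated until the participant can complete the prescribed work". The text does not say whether missed repetitions are made up, or how the rule runs across the two trials.
- **What is kept the same:** "the exercised and non-exercised leg will be the same between trials". No load, number of repetitions or total work is carried over.
- **When the dose is given:** biopsies follow the bout, and then "Immediately after the biopsies, volunteers will consume the appropriate dose".

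On design, B5.1 states: "This study will be a randomized, double-blind, cross-over controlled trial". On allocation it says only that a team member "will generate the randomization scheme using a random number generator"; equal numbers in the two dose orders are not stated.

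The trials are 14 days apart. Under 3-d Run-In and 5-d Energy Deficit, "Routine physical activity (exercise) can be resumed during the wash-out phase", and the rest of that sentence holds it to the level each volunteer reported before the study. B5.8.2 plans an ANOVA for the effect of dose and names no term for period, sequence or exercise work.

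**The concern.** The post-exercise dose effect is a within-volunteer difference, so it is cleanest when the leg receives the same stimulus on both days. Section B2 (Molecular Regulation of Skeletal Muscle Anabolism) says that resistance exercise can by itself activate mTORC1 and, in the end, FSR. A volunteer whose load is cut twice in one trial and not at all in the other therefore contributes a difference that may partly reflect work rather than dose.

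The number and timing of cuts could well differ. The same leg repeats a heavy bout, both bouts start from one earlier 1RM, and nothing asks trial 2 to reproduce what was completed in trial 1.

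The stake is precision in the post-exercise half of the hypotheses in B4, including muscle protein synthesis, which B5.1 names as a primary outcome. Diet, prior activity and leg are all controlled, while completed work is not. Without a log, unequal work could not be seen or examined afterwards.

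**Working it through.** **1. The plan's own figure.** B5.8.1 gives a difference of 0.015 %/h, SD 0.02 %/h and alpha 0.05, for the rested and the exercised leg alike. Reading the SD as that of the paired difference, with a two-sided paired t-test (noncentral t, noncentrality = (0.015/0.02) × √n):

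- n = 16 gives 80.1% power, matching the stated 16 for 80%.
- n = 20 gives 88.9%, close to the stated 90%.

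**2. Size of one load step.** The documents give no 1RMs and no frequency of reductions, so the 1RMs below are assumptions. Share of one exercise's load = 4.5 / (0.8 × 1RM).

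| Exercise | Assumed 1RM (kg) | 80% load (kg) | One 4.5-kg step |
|---|---|---|---|
| Leg extension | 40 | 32 | 14.1% |
| Leg extension | 60 | 48 | 9.4% |
| Leg extension | 80 | 64 | 7.0% |
| Leg press | 150 | 120 | 3.75% |
| Leg press | 200 | 160 | 2.8% |

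Both exercises have the same sets and repetitions, so one leg-extension step over all eight sets, as a share of total load × repetitions, is:

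- 4.5 / (32 + 120) = 3.0%
- 4.5 / (64 + 160) = 2.0%

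If the cut comes from set 5 onward, these halve to 1.5% and 1.0%. Further steps add in proportion. Nothing in the documents converts a work difference into an FSR difference.

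**3. Is there a systematic link with dose?** That day's load cuts happen before that day's drink, and dose order is randomized and blinded. The expected work difference between doses is therefore zero. A simulation with no dose effect and an assumed order effect of 0 to 0.010 %/h gave a mean estimated dose difference of about 0. Type I error was 0.049–0.051 under simple randomization and 0.028–0.050 with a 10:10 split.

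**4. Cost in noise.** Let unequal work add an assumed SD s to the paired FSR difference, so that the total SD = √(0.02² + s²).

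| s (%/h) | Total SD | Power at n = 20 | n for 80% |
|---|---|---|---|
| 0 | 0.0200 | 88.9% | 16 |
| 0.005 | 0.0206 | 87.0% | 17 |
| 0.010 | 0.0224 | 81.2% | 20 |
| 0.015 | 0.0250 | 72.1% | 24 |

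Part of s may already sit within the planned 0.02, so these rows are illustrative.

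**5. Cost of an order effect.** Let p be the average FSR shift from trial 1 to trial 2, and let k of the 20 volunteers take the high dose second. The unadjusted dose difference then shifts by p × (2k/20 − 1).

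- At 10:10 the shift is 0.
- At 13:7 it is 0.3p: 0.0015 %/h for p = 0.005 and 0.0030 %/h for p = 0.010. That is 10% and 20% of the 0.015 %/h target.
- Under simple randomization, a split of 13:7 or worse has probability 0.26.

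With a period term the standard error is 0.02 × √(1/k + 1/(20 − k)) / 2 on 18 degrees of freedom. Power is 88.7% at 10:10 and 85.7% at 13:7, whatever p is. Without the term, at 10:10, power falls to 86.9% for p = 0.005 and 80.8% for p = 0.010, because the order effect inflates the residual.

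**The case against.** A reader might infer that EAA dose is confounded with exercise stimulus. The documents do not support that: the bout and biopsies come before the drink, and the order is randomized and double-blind, so a dose cannot cause that day's load cuts. This part of the defence stands in full.

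A reader might also take the 7–14% as the change in exercise stimulus. It describes one of two exercises, on assumed 1RMs, with the cut in force for every set. On total work the figure is 2–3%, or 1–1.5% for a cut from set 5.

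Other points for the plan:

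- **The restart is inferred.** That the reduction rule begins again in each trial is the natural reading, not an explicit statement. The rule refers to a cited study not available here. The figures and the pages before Section B were also not available, so a matching rule there cannot be excluded.
- **Drift is limited.** Washout exercise is held to pre-study levels, with logs every third day reviewed by dietitians. Non-study activity is restricted before both trials. C6.1 has volunteers familiarized with the tests and protocol well in advance, and B5.2.3 requires six months of resistance training. No order effect is demonstrated.
- **There is some slack.** B5.8.1 raises n from 16 to 20 partly for greater variability. That covers an extra SD of up to about 0.010 %/h at 80% power, though no longer at the stated 90%.
- **Equal absolute load is a choice.** Equal relative effort is a legitimate alternative. But the visible plan starts from one earlier 1RM, so repeating trial 1 loads fits what it already does.

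These points reduce the expected size. They do not supply a record of completed work, balanced sequences or a period term.

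**Conclusion.** The point holds as a minor precision and recording gap. Followed as written, the load rule allows unequal work in a within-volunteer comparison, and the visible text neither matches that work between trials nor records it. The consequence is possible added noise in exercised-leg FSR and signalling and in whole-body measures taken after the bout. An average order effect is also possible, and it cancels only if the two sequences are balanced or period is modelled; the plan states neither. The rested leg is less exposed.

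The size cannot be fixed from the documents. If the extra SD is 0.005 %/h, the loss is about 2 points of power; at 0.010 %/h most of the margin gained by going from 16 to 20 volunteers is gone. Both values are assumptions, as are the 1RMs and the order effects. The conclusion also rests on reading the planned SD as that of the paired difference, which reproduces the stated sample size.

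**What to change.** In B5.3:

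1. Log load and completed repetitions for every set in trial 1.
2. Prescribe the same set-by-set loads for the same leg in trial 2, keeping the existing reduction rule only for a volunteer who cannot repeat them.
3. Log trial 2 in the same way, and report completed work (load × repetitions) by trial and by dose, with the paired difference.

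In B5.8.2, include period in the dose model. The period term removes an average order effect but not volunteer-level differences in work, so the log is needed as well.

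**Cost:** a sentence or two in B5.3, a load log on the exercise form, and one model term. A volunteer who is stronger in trial 2 will work at a slightly lower relative intensity. The period term costs a little power when there is no order effect: 88.9% to 88.7% with a 10:10 split, or to 85.7% at 13:7. The fallback still allows some unequal work, but it would then be visible.

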**Figure 6. Infusion Protocol**

enriched with L-[ring-H5]-phenylalanine to 4% to limit potential disturbances in isotopic steady-state. Volunteers will remain rested during serial blood sampling over a 3-h period following ingestion. Final biopsies will be taken from each leg at the end of the 3-h period. There will be a total of 2 incisions per EAA trial, one on the rested leg and one on the exercised leg. A total of 5 muscle biopsies will be collected from each volunteer per EAA trial; 2 through 1 incision on the exercised leg and 3 through 1 incision on the rested leg (2 new incisions will be made on the subsequent EAA trial. The incisions on EAA trial 1 will NOT be used for trial 2). Blood samples will be collected at regular intervals to assess isotopic enrichments for kinetic calculations, insulin, blood urea nitrogen, and amino acid concentrations (**Figure 6**).

### **3-d Run-In and 5-d Energy Deficit**

Volunteers will complete a baseline, pre-study 3-d diet record (**Appendix A**) and a 3-d activity log (**Appendix B**) according to instructions provided by study team dietitians. The data will be analyzed using Food Processor SQL™ (Salem, OR Version 10.0) and collected to predict volunteers' total daily energy requirements for the 3-d eucaloric run-in and 5-d energy deficit diets. The volunteers will receive standardized meals derived primarily from military combat rations (Meals Ready-to-Eat, MRE) for each diet phase to replicate the source of nutrition during short-term military operations. The energy content and macronutrient distribution of the MRE-based, 3-d run-in diet will be sufficient to maintain body weight and provide between 50-65% carbohydrate and  $1.6 \pm 0.2$  g protein·kg·d, amounts habitually consumed by Warfighters in past USARIEM studies [39, 42]. Total energy content of the 5-d energy deficient diet will be reduced by 30%, primarily by reducing the total amounts of carbohydrate and fat consumed, while keeping dietary protein constant at  $1.6 \pm 0.2$  g protein·kg·d. All meals will be prepared and provided to volunteers by study team dietitians during the 3-d run-in diet. During the 5-d energy deficit, all meals will be prepared and provided to the volunteers.. Volunteers will be completely restricted from all non-study physical activity during the 3-d run-in and 5-d energy deficit diets to minimize complications and the potential for carryover effects on study parameters. If necessary, military volunteers will be provided study-specific profiles to restrict physical activity. This approach has been applied successfully in past USARIEM studies [39].

During the 14-d washout period, volunteers will be instructed to consume an ad libitum diet. Routine physical activity (exercise) can be resumed during the wash-out phase at levels consistent with amounts reported in pre-study 3-d activity records. Diet records (24-h) and activity logs (24-h) will be completed every third day and then reviewed (the following day) during the 14-d washout period to assess dietary intake and physical activity. Volunteers will meet with study dietitians to review these records.

### **Anthropometric Data**

Anthropometrics, performed using standardized techniques and equipment, will be used to characterize study volunteers, and evaluate responses to each 5-d energy deficit. Height will be measured in duplicate to the nearest 0.1 cm using a stadiometer at baseline. Body weight will be measured, nude (scale will be placed in a locked bathroom) and after an overnight fast ( $\geq 8$  h), using a calibrated digital scale to the nearest 0.1 kg at baseline and then daily during each 3-d run-in and 5-d energy deficit period to ensure weight maintenance and/or weight loss. Body mass will be measured every third day during the 14-d washout period (measurements will correspond with the days diet records and activity logs are reviewed described above).

Body composition will be determined at baseline and after the 14-d washout by using a dual energy x-ray absorptiometry (DEXA, DPX-IQ, GE Lunar Corporation, Madison, WI). The DEXA technique allows for the non-invasive assessment of soft tissue composition by region with a precision of 1-3%. The volunteer will lay face-up on the DEXA densitometer table in shorts, t-shirts, and stocking feet, and will be asked to remain motionless for the 8-10 min scan. These data will be used to calculate total body mass, fat-free mass, and fat mass. Calibration to external standards will be performed before actual data collection. The operator remains in the room with the volunteer during the scan.

